Document Type:	Study Protocol
Official Title:	Study on the A ssociation of Uterine P erforation and IUD E xpulsion With Breastfeeding Status at the Time o f IUD Insertion and Postpartum Timing of IUD Insertion in Electronic Medical Record Databases - A Postmarketing Requirement for Mirena (APEX IUD)
NCT Number:	NCT03754556
Document Date:	29 Jun 2018

Observational/Post Authorization Study Information

Title	Study on the A ssociation of Uterine P erforation and IUD E xpulsion With Breastfeeding Status at the Time of I UD Insertion and Postpartum Timing of IUD Insertion in Electronic Medical Record Databases – A Postmarketing Requirement for Mirena (APEX IUD)
Protocol version identifier	Version 2.0 (protocol amendment)
Date of last version of protocol	29 June 2018
IMPACT study number	19682
Study type/Study phase	 non-PASS  PASS Joint PASS:  YES  NO Phase IV
Active substance	Intrauterine contraceptives: Plastic IUD with progestogen (ATC code G02BA03) and Plastic IUD with copper (ATC code G02BA02)
Medicinal product	Mirena®, Skyla®, Liletta®, Kyleena®, and ParaGard® intrauterine devices
Marketing authorization holder(s)	Bayer AG, 13342 Berlin
Research question and objectives	
United States postmarketing requirement study assessing outcomes of uterine perforation and intrauterine device (IUD) expulsion in association with breastfeeding, postpartum exposures, and type of IUD.
 
The study aims to quantify the risk of uterine perforation and IUD expulsion for the following comparisons:
 
 • Women who are breastfeeding at the time of IUD insertion versus not breastfeeding at the time of IUD insertion • Women who had a first observed IUD insertion within different time periods postpartum (i.e., ≤ 6 weeks, > 6 weeks and ≤ 14 weeks, > 14 weeks and ≤ 52 weeks) versus women who had their first observed IUD insertion more than 52 weeks postpartum, including women without a recorded delivery within the past 52 weeks

4.1 Title

Study on the Association of Uterine Perforation and IUD Expulsion With Breastfeeding Status at the Time of IUD Insertion and Postpartum Timing of IUD Insertion in Electronic Medical Record Databases – A Postmarketing Requirement for Mirena (APEX IUD)

4.2 Rationale and background

Mirena, a levonorgestrel (LNG)-releasing intrauterine system, was approved for use in the United States (US) in December 2000 (Bayer HealthCare Pharmaceuticals Inc., 2015). In August 2015, Bayer received a postmarketing requirement from the US Food and Drug Administration (FDA) to evaluate the incidence of and risk factors for uterine perforation in patients receiving Mirena intrauterine devices (IUDs) (communication from FDA to Bayer, 18 August 2015). The concerns described by the FDA, based on information from the European Active Surveillance Study for Intrauterine Devices (EURAS-IUD), were that insertion of the IUD immediately postpartum might result in a higher risk of uterine perforation and that breastfeeding at the time of IUD insertion might be associated with higher risk of uterine perforation.

In response, on October 16, 2015 [see NDA 21, 255, seq 0096], Bayer proposed to conduct a retrospective, cohort study of women with an intrauterine system or copper IUD using electronic health record (EHR) databases and included information on three potential electronic data sources to support this approach. In May 2016, the FDA responded favorably to Bayer’s proposal and indicated in September 2016 that use of the retrospective approach was pending successful results

from a validation/feasibility study that should be submitted before the postmarketing requirement study, to support the proposed retrospective study within the EHR setting. A validation study has been conducted within four* EHR databases and has indicated that uterine perforation, IUD[†] expulsion, and breastfeeding can be adequately identified within these data sources.

The study described within this protocol is a retrospective postmarketing requirement study assessing outcomes of uterine perforation and IUD expulsion in association with breastfeeding and postpartum exposures in the EHR databases, as requested by the FDA.

4.3 Research question and objectives

The overall goal of this study is to assess the impact of breastfeeding and timing of postpartum IUD insertion on uterine perforation and IUD expulsion in a population of US women. The study aims to quantify the difference in risk of perforation and expulsion in the following groups:

- Women who are breastfeeding at the time of IUD insertion versus not breastfeeding at the time of IUD insertion
- Women who had a first observed IUD insertion within different time periods postpartum (i.e., ≤ 6 weeks, > 6 weeks and ≤ 14 weeks, > 14 weeks and ≤ 52 weeks) versus women who had their first observed IUD insertion more than 52 weeks postpartum, including women without a recorded delivery within the past 52 weeks

This study will also assess the difference in risk of perforation and expulsion by type of IUD. In addition, this study aims to assess the following interactions:

- The extent to which breastfeeding status modifies the association of perforation and/or expulsion for women with IUD insertion at different time periods postpartum (i.e., IUD insertion ≤ 14 weeks versus IUD insertion > 14 weeks postpartum) among women with recorded delivery within the past 52 weeks
- The extent to which type of IUD (LNG-releasing vs. copper IUD) modifies the association of perforation and/or expulsion with breastfeeding status and/or postpartum status

Approximately 10% of IUD insertions in the databases are expected to occur in women who have previous exposure to an IUD within the data. For most analyses, only the first IUD insertion observed in the database will be included in order to maintain independence of observations. Multiple insertions will be considered only for objectives 18 and 26 (see Section 4.3.2).

The study includes the following primary and secondary objectives. The secondary objectives are grouped by type of analysis (rates, comparative, interaction) and outcome (uterine perforation, IUD expulsion, indicators of difficult insertion).

* Fourth data source added to incorporate women not on the west coast and not in the Kaiser Permanente health care system. Inclusion of this data source increases understanding of generalizability of the study results.

[†] From this point forward throughout the protocol, both LNG-releasing intrauterine systems and copper IUDs will be referenced as "IUD."

4.3.1 Primary objectives

1. To evaluate whether the risk of uterine perforation among women who were breastfeeding at the time of first observed IUD insertion differs from the risk of uterine perforation among women who were not breastfeeding at the time of first observed IUD insertion
2. To evaluate whether the risk of uterine perforation among women who had a first observed IUD insertion within different time periods postpartum (i.e., ≤ 6 weeks, > 6 weeks and ≤ 14 weeks, > 14 weeks and ≤ 52 weeks) differs from the risk of uterine perforation among women who had their first observed IUD insertion more than 52 weeks postpartum, including women without a recorded delivery within the past 52 weeks

These primary objectives will include modification by the data source (i.e., interaction terms) if preliminary testing indicates statistically significant interaction between data source and breastfeeding (objective 1) or timing of postpartum insertion (objective 2). For each data source, interaction terms will be included only for the objective(s) with statistically significant interaction(s).

4.3.2 Secondary objective(s)

Rates: uterine perforation

3. To estimate the incidence rate and cumulative incidence of uterine perforation among women using IUDs
4. To estimate the incidence rate and cumulative incidence of uterine perforation among women using IUDs for the following categories:
 - ≤ 6 weeks postpartum
 - > 6 weeks and ≤ 14 weeks postpartum
 - > 14 weeks and ≤ 52 weeks postpartum
 - > 52 weeks postpartum, including women without recorded delivery within the past 52 weeks
 - ≤ 14 weeks postpartum
 - > 14 weeks postpartum, including women without recorded delivery within the past 52 weeks
 - ≤ 36 weeks postpartum
 - > 36 weeks postpartum, including women without recorded delivery within the past 52 weeks
5. To estimate the incidence rate and cumulative incidence of uterine perforation among women who were and were not breastfeeding at the time of IUD insertion
6. To estimate the incidence rate and cumulative incidence of uterine perforation among women with different types of IUD (i.e., LNG-IUD and copper IUD)
7. To estimate the incidence rate and cumulative incidence of uterine perforation among women with and without menorrhagia (heavy menstrual bleeding) in the 12 months before IUD insertion

Rates: IUD expulsion

8. To estimate the incidence rate and cumulative incidence of IUD expulsion among users of IUDs
9. To estimate the incidence rate and cumulative incidence of IUD expulsion among users of IUDs for the following categories:
 - ≤ 6 weeks postpartum
 - > 6 weeks and ≤ 14 weeks postpartum
 - > 14 weeks and ≤ 52 weeks postpartum
 - > 52 weeks postpartum, including women without recorded delivery within the past 52 weeks
 - ≤ 14 weeks postpartum
 - > 14 weeks postpartum, including women without recorded delivery within the past 52 weeks
 - ≤ 36 weeks postpartum
 - > 36 weeks postpartum, including women without recorded delivery within the past 52 weeks
10. To estimate the incidence rate and cumulative incidence of IUD expulsion among women who were and were not breastfeeding at the time of IUD insertion
11. To estimate the incidence rate and cumulative incidence of IUD expulsion among women with different types of IUD (i.e., LNG-IUD and copper IUD)
12. To estimate the incidence rate and cumulative incidence of IUD expulsion among women with and without menorrhagia in the 12 months before IUD insertion

Prevalence of difficult IUD insertion

13. To describe the prevalence of indicators of a difficult IUD insertion (e.g., need for cervical dilation or ultrasound guidance, clinician experience) among all users

Comparative: uterine perforation

14. To estimate the adjusted hazard ratio of uterine perforation among women who had a first observed IUD insertion early in the postpartum period (i.e., up to 14 weeks postpartum) versus those who had a first observed IUD insertion late in the postpartum period (i.e., more than 14 weeks postpartum, including women without recorded delivery within the past 52 weeks)
15. To estimate the adjusted hazard ratio of uterine perforation among women who had a first observed IUD insertion ≤ 36 weeks postpartum versus women who had a first observed IUD insertion > 36 weeks postpartum, including women without recorded delivery within the past 52 weeks (this objective will be performed as a sensitivity analysis; same cut point as in EURAS-IUD)
16. To estimate the adjusted hazard ratio of uterine perforation for women whose first observed IUD was a copper IUD versus women whose first observed IUD was an LNG-releasing IUD
17. To estimate the adjusted incidence rate ratio (IRR) and incidence rate difference (IRD) of uterine perforation at 1 year and 5 years of follow-up among women who had a first observed IUD insertion ≤ 36 weeks postpartum versus women who had a first observed IUD

- insertion > 36 weeks postpartum, including women without recorded delivery within the past 52 weeks (same analytic approach as EURAS-IUD)
18. To estimate the adjusted hazard ratios of uterine perforation described in objectives 1, 2, and 14-16 across all subsequent insertions (i.e., not the first insertion) observed within the data. (The site-specific analyses will be performed only if there are more than 20,000 subsequent IUD insertions for that site. The pooled analysis will include all sites regardless of the number of subsequent IUD insertions at a site.)
 19. To estimate the adjusted hazard ratio of uterine perforation for women using an IUD who have at least one diagnosis code indicating menorrhagia in the 12 months before IUD insertion versus IUD users who do not have this indication (this analysis will be performed only if there are more than 20,000 IUD users with an indication of menorrhagia that can be included in the analysis)

Comparative: IUD expulsion

20. To estimate the adjusted hazard ratio of IUD expulsion among women who were breastfeeding at the time of first observed IUD insertion versus those who were not breastfeeding at the time of first observed IUD insertion
21. To estimate the adjusted hazard ratio of IUD expulsion for women who had a first observed IUD insertion early in the postpartum period (i.e., up to 14 weeks postpartum) versus those who had a first observed IUD insertion late in the postpartum period (i.e., more than 14 weeks postpartum, including women without recorded delivery within the past 52 weeks)
22. To estimate the adjusted hazard ratio of IUD expulsion for women who had a first observed IUD insertion ≤ 36 weeks postpartum versus women who had a first observed IUD insertion > 36 weeks postpartum, including women without recorded delivery in the past 52 weeks
23. To estimate the adjusted hazard ratios of IUD expulsion for women who had a first observed IUD insertion in early postpartum categories versus women who had a first observed IUD insertion late in the postpartum period, using the following strata:
 - ≤ 6 weeks postpartum
 - > 6 weeks and ≤ 14 weeks postpartum
 - > 14 weeks and ≤ 52 weeks postpartum
 - > 52 weeks postpartum, including women without recorded delivery in the past 52 weeks (referent category)
24. To estimate the adjusted hazard ratio for IUD expulsion for women whose first observed IUD was an LNG-releasing IUD versus women whose first observed IUD was a copper IUD
25. To estimate the adjusted IRR and IRD of IUD expulsion at 1 year and 5 years of follow-up among women who had a first observed IUD insertion ≤ 36 weeks postpartum versus women who had a first observed IUD insertion > 36 weeks postpartum, including women without recorded delivery within the past 52 weeks
26. To estimate the adjusted hazard ratios of IUD expulsion described in objectives 20-24 across all subsequent insertions (i.e., not the first insertion) observed within the data. (The site-specific analyses will be performed only if there are more than 20,000 subsequent IUD insertions for that site. The pooled analysis will include all sites regardless of the number of subsequent IUD insertions at a site.)

27. To estimate the adjusted hazard ratio of IUD expulsion for women using an IUD who have at least one diagnosis code indicating menorrhagia in the 12 months before IUD insertion versus IUD users who do not have this indication (this analysis will be done only if there are more than 20,000 IUD users with an indication of menorrhagia that can be included in the analysis)

Interactions (effect modification)

28. To evaluate the extent to which breastfeeding status (yes vs. no) modifies the observed association of uterine perforation for women with IUD insertion at different time periods postpartum (i.e., IUD insertion \leq 14 weeks versus IUD insertion $>$ 14 weeks postpartum) among women with a recorded delivery within the past 52 weeks) at the time of the first observed IUD insertion
29. To evaluate the extent to which type of IUD (LNG-IUD vs. copper IUD) modifies the association between uterine perforation among women who were and were not breastfeeding at the time of first observed IUD insertion
30. To evaluate the extent to which type of IUD (LNG-IUD vs. copper IUD) modifies the association between IUD expulsion among women who were and were not breastfeeding at the time of first observed IUD insertion
31. To evaluate the extent to which type of IUD (LNG-IUD vs. copper IUD) modifies the association of uterine perforation for women with IUD insertion at different time periods postpartum (i.e., \leq 6 weeks, $>$ 6 and \leq 14 weeks, $>$ 14 and \leq 52 weeks) versus IUD insertion more than 52 weeks postpartum, including no recorded delivery within the past 52 weeks at the time of the first observed IUD insertion
32. To evaluate the extent to which type of IUD (LNG-IUD vs. copper IUD) modifies the association of IUD expulsion for women with IUD insertion at different time periods postpartum (i.e., \leq 6 weeks, $>$ 6 and \leq 14 weeks, $>$ 14 and \leq 52 weeks) versus IUD insertion more than 52 weeks postpartum, including no recorded delivery within the past 52 weeks at the time of the first observed IUD insertion

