4.8 Study size

Uterine perforation is an uncommon event; 1.3 cases per 1,000 IUD insertions were reported in the EURAS-IUD at 1-year follow-up (Heinemann et al., 2015). The EURAS-IUD also showed that the incidence was higher in breastfeeding women and with early (≤ 36 weeks) postpartum insertion.

Based on results from the validation/feasibility study, the expected number of women with insertion of an IUD available through 30 June 2018, from the four health care systems is approximately $N = 225,000$, with breastfeeding status available for approximately 60,000 of the total. For the two primary objectives related to the risk of uterine perforation, the power of the study is based on detecting a difference in the estimated risk of uterine perforation with respect to (1) breastfeeding status at the time of IUD insertion and (2) time of IUD insertion after pregnancy delivery. The null hypothesis is no difference in risk of perforation by breastfeeding or time of IUD insertion. There will be no adjustment for multiplicity.

For a two-sided test of the hazard ratio (Schoenfeld, 1983), based on a perforation risk of 1.3 per 1,000 insertions in the 1 year after insertion, a hazard ratio of 2.0 can be detected at the two-sided $\alpha = 0.05$ significance level with the following power:

- 85% for breastfeeding versus not breastfeeding (assuming 60% of women with available breastfeeding status are breastfeeding)
- 73% for ≤ 6 weeks, > 99% for > 6 and ≤ 14 weeks, and 73% for > 14 and ≤ 52 weeks versus > 52 weeks postpartum IUD insertion (assuming a postpartum period allocation of 5:20:5:70)

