4.10 Milestones

This study is planned for 78 weeks from the time of FDA approval of this protocol to allow adequate time for development of the statistical analysis plan, data extraction, development of algorithms for additional variables, testing of variables for inclusion in and development of propensity scores, analysis at each site, pooled analysis of results from each site, and writing the study report.

5. Amendments and updates

Number	Date	Section of study protocol	Amendment	Reason
1	29 Jun 2018	Sections 4.3.1 and 8.1	Modified primary objectives such that postpartum exposure has four categories, and assessment of database interactions are included within analysis for primary objectives	Requested by FDA
2	29 Jun 2018	Sections 4.3.2 and 8.2	Modified secondary objectives for interactions to use (1) four categories of postpartum exposure when assessing potential effect modification of IUD type and (2) two categories of postpartum exposure when assessing potential effect modification of breastfeeding and postpartum exposure	Requested by FDA

Number	Date	Section of study protocol	Amendment	Reason
3	29 Jun 2018	Sections 4.3.2 and 8.2	Added objectives to compare outcomes among women with and without documentation of menorrhagia (heavy menstrual bleeding) up to 1 year before IUD insertion	Requested by FDA
4	29 Jun 2018	Section 9.9	Added wording regarding reliability assessment of ICD-10-CM diagnosis codes for outcomes	Requested by FDA
5	29 Jun 2018	Section 9.7.1.3.2 and 9.7.3.3.3	Clarified cohorts of interest and propensity score development for all applicable analyses	Requested by FDA
6	29 Jun 2018	Sections 4.3.2 and 8.2	Removed objectives related to assessments of IUD brand	Due to changes in data sharing expectations between research partners and Bayer

6. Milestones

Table 1. Milestones

Milestone	Planned date
Protocol and validation study results submitted to the FDA	September 2017
Submission of revised protocol and statistical analysis plan	June 2018
Last date of data in data pull	30 June 2018 ^a
Study start (anticipated date of FDA approval of protocol)	30 September 2018

^a Initiation of full study is contingent upon FDA approval of the validation study results and revised protocol.

Note: Final report submission is contingent on study start date. To complete the study, 18 months are anticipated between start date and final report.

7. Rationale and background

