There were approximately 325,000 IUD insertions identified during the time frame of the validation/feasibility study (i.e., end date, 30 September 2015), and approximately 65% of those occurred after at least 12 months within the data source. In approximately 90% of IUD insertions, this was the first observed insertion for each woman. Approximately 30% of women were identified as having an IUD inserted within the first 52 weeks postpartum. Based on these results and assumptions—approximately three additional years of data more than the validation study and allowing for a loss of approximately 15% of the insertions due to missing data and the propensity score trimming process (Section 9.7.1.3.2)—the number of first insertions of an IUD available through June 2018 from the four health care systems is anticipated to be approximately 225,000, with breastfeeding status available for approximately 60,000. For the two primary objectives related to the risk of uterine perforation, the power of the study is calculated for differences in the estimated risk of uterine perforation with respect to (1) breastfeeding status at the time of IUD insertion and (2) time interval of the IUD insertion following delivery. The null hypothesis to be tested for primary objective 1 is that the natural logarithm of the adjusted summary perforation hazard ratio for breastfeeding versus not breastfeeding at the time of IUD insertion is equal to 0. Using information from validation study, the expected allocation ratio of breastfeeding versus not breastfeeding is 60:40 for this objective. Three null hypotheses to be tested for primary objective 2 are that the natural logarithm of the adjusted summary perforation hazard ratio for early (i.e., ≤ 6 weeks postpartum, > 6 and ≤ 14 weeks, > 14 and < 52 weeks) versus later (i.e., > 52 weeks) postpartum IUD insertion is equal to 0. Based on information from the validation study, the expected allocation ratio of the corresponding postpartum period categories is 5:20:5:70 for this objective.

Power calculations for the expected number of IUD insertions were performed using PASS 14 software (NCSS, LLC, Kaysville, Utah) for a two-sided test of the hazard ratio (Schoenfeld, 1983). Table 4 indicates the power to detect various hazard ratios at the two-sided $\alpha = 0.05$ significance

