6.2.2.2 Comparing Adjusted Hazard Ratios Among First Observed IUD Insertions

Adjusted hazard ratios associated with the first observed IUD insertions will be estimated for secondary objectives 14-16, and 19 using the same analysis approach (i.e., overlap weighting) as described in Section 6.2.1, with the following exceptions.

1. For type of IUD, analyses may be conducted by data source. However, due to data source restrictions, any results on type of IUD by data source will not be reported.
2. For secondary objectives that include dichotomization of “early” and “late” postpartum categories, separate propensity score models will not be developed. Rather, the propensity score model developed for the four-category variable will be used. The propensity score for dichotomous exposed group will be calculated by collapsing multiple categories (e.g., propensity score for ≤ 14 weeks = propensity score for ≤ 6 weeks + propensity score for > 6 to ≤ 14 weeks).
3. The analyses for objective 19 (menorrhagia) will be performed only if more than 20,000 IUD insertions with an indication of menorrhagia can be included in the analysis.

Balance will be assessed between exposure groups prior to and after weighting. Crude hazard ratios will also be reported.

The same set of analysis tables and figures as those created for objective 1 will be generated, except that no sensitivity analyses will be conducted for these secondary objectives.

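### The adjusted menorrhagia hazard ratios (objectives 19 and 27) hang on an unexplained count of more than 20,000 users, a condition that could be dropped from the pooled analyses at little cost

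*Protocol*

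**What the plan says.** Protocol Section 4.3.2, repeated in Section 8.2, makes two secondary comparisons conditional. Objective 19 (menorrhagia and perforation) is to be "performed only if there are more than 20,000 IUD users with an indication of menorrhagia that can be included in the analysis". Objective 27 (menorrhagia and expulsion) is to be "done only if there are more than 20,000 IUD users with an indication of menorrhagia". SAP Section 2.2 repeats both conditions. SAP Section 6.2.2.2 says that the analyses for objective 19 "will be performed only if more than 20,000 IUD insertions with an indication of menorrhagia can be included in the analysis", and footnote d of SAP Section 9.4 applies the rule to both objectives. The protocol counts users and SAP 6.2.2.2 counts insertions. For first insertions these are the same number, so nothing turns on that.

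The objectives come from amendment 3 in Protocol Section 5: "Added objectives to compare outcomes among women with and without documentation of menorrhagia (heavy menstrual bleeding) up to 1 year before IUD insertion". The reason given there is an FDA request.

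Three other parts of the plan bear on the threshold:

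- **Objectives 18 and 26 (subsequent insertions).** The same figure of 20,000 appears, but it decides only whether site-specific results are produced. The pooled analysis takes in every site at any count.
- **Primary objective 2.** No minimum is set. Protocol Section 4.8 gives power at a hazard ratio of 2.0 as "73% for ≤ 6 weeks, > 99% for > 6 and ≤ 14 weeks", and again 73% for > 14 to ≤ 52 weeks.
- **Objectives 7 and 12.** Crude incidence rates and cumulative incidence by menorrhagia carry no condition.

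**The concern.** A minimum count is a reasonable device if it marks the point below which an estimate is too imprecise to be useful. Nothing in the documents ties 20,000 to such a point. There is no stated rationale, no power figure for menorrhagia and no expected number of women with the diagnosis. The same count serves both outcomes, although Protocol Section 9.7.1.3.2 says that few events are expected, for perforation above all. A count of exposed women that ignores the event rate cannot mark the same precision for both.

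At stake is whether the confounder-adjusted answer is produced at all. If 20,000 or fewer users have menorrhagia, the hazard ratios for both outcomes are dropped, pooled analysis included, and only the crude descriptions of objectives 7 and 12 remain. SAP Section 3 treats menorrhagia as a proxy for indication of use. SAP Section 4.1.5 puts breastfeeding status, postpartum timing and IUD type into the propensity models as standing covariates. By the plan's own reasoning, a crude contrast by menorrhagia would lack the control it considers necessary.

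**Working it through.** **Inputs**

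- First insertions: Protocol Section 9.5 says the number "is anticipated to be approximately 225,000, with breastfeeding status available for approximately 60,000".
- Perforation risk: 1.3 per 1,000 insertions (Protocol Sections 4.8 and 9.5).
- Postpartum allocation: 5:20:5:70 (Protocol Section 9.5).
- Test: two-sided, alpha 0.05, Schoenfeld formula (Protocol Section 9.5).
- Expulsion risk: not given in either document, so assumed below.
- Number of users with menorrhagia: not given, so varied below.

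**Formula.** Power = Φ(√(D·p·(1−p))·ln HR − 1.96), where D is total events and p is the exposed share.

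**Step 1: reproduce the plan's figure.** Table 4, ≤ 6 weeks versus > 52 weeks: D = 168,750 × 0.0013 = 219.4 and p = 5/75 = 0.0667. At HR 2.0, √(219.4 × 0.0622) × 0.693 − 1.96 = 0.60, so power is 72.6%, against the stated 73%. The exposed group is 5% × 225,000 = 11,250 women.

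**Step 2: place the threshold.** 20,000/225,000 = 8.9% of the cohort, and 20,000/11,250 = 1.78 times the exposed count expected in two of the three contrasts of primary objective 2.

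**Step 3: perforation by menorrhagia.** D = 225,000 × 0.0013 = 292.5 and p = users/225,000. The last column is users × 0.0013.

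| Menorrhagia users | p | Power, HR 1.5 | Power, HR 2.0 | Events among users at average risk |
|---|---|---|---|---|
| 5,000 | 0.022 | 17% | 42% | 6.5 |
| 10,000 | 0.044 | 30% | 69% | 13.0 |
| 11,250 | 0.050 | 33% | 73% | 14.6 |
| 15,000 | 0.067 | 41% | 84% | 19.5 |
| 20,000 | 0.089 | 51% | 92% | 26.0 |

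Power at HR 2.0 reaches 80% at about 13,360 users. From about 11,250 to 20,000 users the plan would drop a perforation estimate with at least the power planned for two primary contrasts. Below that range it would not.

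**Step 4: expulsion by menorrhagia, assumed rates.** With 5,000 users, p = 0.0222 and p(1−p) = 0.0217. At HR 1.5:

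| Assumed expulsion risk | D | Power |
|---|---|---|
| 5 per 1,000 | 1,125 | 52% |
| 10 per 1,000 | 2,250 | 81% |
| 30 per 1,000 | 6,750 | > 99% |

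With 20,000 users, power at HR 1.5 is 97% even at 5 per 1,000, compared with 51% for perforation in Step 3. One count therefore means very different precision for the two outcomes.

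**The case against.** A fair defence has five parts.

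- **The count is not absurd for perforation.** At 20,000 users, power is 92% at HR 2.0 but 78% at HR 1.75, and the formula ignores precision lost to overlap weighting. If weighting cost 30% of the information (an assumption; the documents give no figure), power at HR 2.0 would be about 81% with 20,000 users and 58% with 11,250. A cautious count for a rare outcome can be defended. This stands as an argument the sponsor could make, but the documents do not make it, and it does not carry over to expulsion.
- **11,250 is an expected cell size, not a minimum that anyone set.** It follows from postpartum categories that Protocol Section 9.3.2 says the FDA proposed, and it belongs to the least powered primary contrasts. Primary objective 1 has 85% power, which would need about 15,440 menorrhagia users. This stands: the figure shows what the plan is willing to analyse and is not a standard of sufficiency.
- **The FDA approved the protocol with the condition in it** (SAP Section 1.2). A reader might infer that the plan falls short of the FDA request. The documents do not support that; they do not show whether the threshold was discussed.
- **The condition may never bind,** because no menorrhagia count is given. This stands.
- **The rule is prespecified and looks only at exposure.** A reader might suspect outcome-driven selection, but nothing in the rule allows it.

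**Conclusion.** The point holds in a limited form. The 20,000 condition is unexplained, is the same for two outcomes of different frequency, and is stricter than the plan's practice for the pooled analyses of objectives 18 and 26 and for primary objective 2. Its effect is conditional: nothing is lost unless 20,000 or fewer of about 225,000 women have menorrhagia.

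If it binds, the loss for perforation is an estimate of 73% to 92% power at HR 2.0 when there are about 11,250 to 20,000 users. A reader might infer that adequately powered perforation estimates are thrown away at any count from 5,000 upward. They are not: power is 42% at 5,000 and 69% at 10,000. For expulsion the loss could begin at smaller counts, but that rests on an assumed rate, and at 5 per 1,000 with 5,000 users power at HR 1.5 is only 52%.

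Nor does a missed threshold leave menorrhagia unreported, since the crude rates and cumulative incidence remain. It is also not certain that propensity models 4 and 8 would go unbuilt: SAP Section 9.3 lists them without a condition, and only the analyses for objectives 19 and 27 are made conditional.

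These figures rest on the protocol's own cohort size, perforation risk and formula, with no allowance for weighting. The Protocol Section 9.5 tables make none either, so the comparison is like for like. Severity is low: this is a cheap improvement to two of 30 secondary objectives.

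**What to change.** Remove the 20,000 condition from the pooled analyses of objectives 19 and 27, as the plan already does for the pooled analyses of objectives 18 and 26. Report each adjusted hazard ratio with its 95% confidence interval and the number of events in each menorrhagia group, so that precision is visible and needs no cutoff. Do not put 11,250 in place of 20,000, because that would be another count unrelated to events. A count condition may stay for site-level results if the sponsor wants one.

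The text to amend is Protocol Sections 4.3.2 and 8.2, and SAP Sections 2.2, 6.2.2.2 and 9.4 (footnote d).

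The cost is wording. Propensity models 4 and 8 are already specified, and the same tables and figures are already planned. The downside is a possibly wide confidence interval for perforation if menorrhagia is uncommon: at the average risk, 5,000 users would contribute only about 6.5 events.
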